1.1 Summary of document

1.1.1 Scope

The statistical analysis plan for the CARDIOMAN study has been written in accordance with BTC standard operating procedures, the CONSORT statement, and International Conference on Harmonisation (ICH) Statistical Principles for Clinical Trials E9, by [name], Medical Statistician / Senior Research Associate at BTC, under the supervision of [name], Director of BTC, and covers all final statistical analyses to be performed, outlined in the study protocol found study master file.

1.1.2 Planned analyses and dissemination

An end of study report will be produced once phase 2 of the study has finished, once the second 4 month treatment phase has finished and outcome data collected, and will be disseminated to the TMG when all pre-specified final analyses have been performed. An independent joint data monitoring and safety committee and trial steering committee (DMSC/TSC) will review the safety and ethics of the study. Short blinded study update reports including safety and compliance will be produced and disseminated at regular intervals during the study. The DMSC/TSC have the authority to recommend that the study stops if deemed necessary based on the observed data.

1.2 Background of study

1.2.1 Summary

Barth syndrome is a rare, life threatening, genetic disease which affects young males. It is caused by abnormal fats (lipids) in the powerhouses of cells (mitochondria) and those who suffer with it often develop heart failure, heart rhythm abnormalities, bacterial infections, poor growth or feeding, weak muscles, developmental delay, severe exercise intolerance, lethargy and fatigue; all of which affect their daily life. Low white blood cell counts occur frequently due to intermittent or persistent reduction in numbers of the neutrophils that are responsible for fighting bacterial infections. This requires expensive and distressing injections to stimulate the bone marrow to produce more neutrophils. In addition, approximately one third of all males living with this disease in the UK have required heart transplantation.

Scientific research has shown that several treatments can improve the fat abnormalities in cells affected by Barth syndrome from either mice or humans; one of which is a drug called bezafibrate. Bezafibrate is particularly attractive as it has been safely administered for over 20 years in the UK to both adults and children for the treatment of high blood fats. The purpose of this study is to see if bezafibrate can be given safely and effectively to people with Barth syndrome in a blinded randomised trial.

Bezafibrate or an inactive (placebo) treatment will be given for 4 months, followed by a one month break, and then followed by 4 months of the alternate treatment (e.g. placebo if bezafibrate taken for the first 4 months and vice versa). Half of the participants will take bezafibrate first, the other half will take placebo first; participants and research staff will not know which order the treatments are given in (double-blind trial).

Once the participants have completed the first phase of treatment, the study statistician will be unblinded to the treatment arms and will then assess whether or not there is evidence of efficacy of bezafibrate for the primary outcome.

Tests will be performed at commencement of the study and after each 4 month treatment period, looking for benefit in blood cells, exercise capacity, heart function or quality of life. The clinical studies of bezafibrate will run alongside laboratory work at Bristol University and Great Ormond St Hospital to see the effect of bezafibrate on participant's cells and mitochondria (powerful electron microscopes show that these are abnormal in Barth syndrome). This is to see whether we can predict any improvement in symptoms in order to tell us which patients would benefit from this treatment in future. Laboratory work will also be carried out on participant's cells using another drug called resveratrol, which has also shown promise in laboratory tests, to see if this could provide an alternative treatment.

We wish to study up to 18 Barth syndrome boys and young men; all of those with Barth syndrome in the UK aged 6 years or over. We aim to use a national children's research network and/or local GPs to perform monthly blood tests in order to minimise the amount of travel to Bristol for participants. Safety will be monitored by an independent committee with the authority to recommend stoppage if obvious problems are seen.

If promising results are obtained with either or both drugs, we would share this information with American/European teams so that this work will have worldwide benefit. For this, we have the complete backing of our patients, their families and the respective UK and USA charities.

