2.2 Randomisation

A randomisation list will be created, numbered by study ID, with a 1:1 ratio of the allocations: bezafibrate followed by placebo, or placebo followed by bezafibrate. The allocation will be according to permuted block randomisation, with blocks of varying size. This list of study IDs and corresponding medication order will be provided to the clinical trials pharmacy department.

N.B. This method of randomisation does not comply with the requirement of an internet-based randomisation system supplied by an MHRA approved provider (e.g. Sealed Envelope) as described in the Bristol CTEU SOP ST 005 'Development of a Randomisation System', but an internet-based system was thought to be prohibitively expensive for so few patients.

Once a participant has given consent and eligibility has been documented and confirmed, they will be allocated to the next consecutive study ID. A doctor will prescribe the study 'medication' and the pharmacy will dispense the appropriate intervention given the participant's study ID and phase of the trial.

Allocation concealment will minimise selection bias. The sequence of random allocations will be generated by computer and will be concealed from all clinical and research personnel.

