2.5 Blinding

All participants, their clinical care team, their research nurse(s) response for follow-up, and all BTC staff will be unaware of the allocation order.

3. Populations

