3.3.2 Per-protocol population

In addition to the ITT analysis, a complier average casual effect (CACE) analysis will be considered for the primary outcome if there are a considerable number of major protocol deviators ($> 20\%$ of participants). The number of protocol deviators and the extent of the protocol deviations will be monitored.

Major protocol deviators include the following:

- Incorrect unblinding procedure
- Any serious breaches to the protocol, defined as those events that affect the confidentiality or safety of participants, or the integrity of the trial
- Participant does not meet the study eligibility criteria, but receives a single dose of study treatment

In order to assess the utility of a per-protocol analysis, the proportion of protocol deviators will be assessed, without reference to outcome data, through a blinded examination of the population at the time of analysis by the study statistician in co-operation with other members of the TMG.

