4.1 General considerations

Statistical analysis is the responsibility of the BTC study statistician and all analyses will be carried out using the most recent version of the statistical software at the time of analysis.

Where treatments are being compared formally using statistical modelling, the placebo group will act as the reference category, in order for interpretations to be in the form: the effect of bezafibrate in comparison with placebo. All applicable statistical tests will be 2-sided and will be performed using a 5% significance level, with the exception of tests for interactions that will be performed using a 10% significance level, and confidence interval will be 95% unless otherwise stated.

No formal adjustment will be made for multiple testing, but consideration will be taken in interpretation of results to reflect the number of statistical tests performed and the consistency, magnitude and direction of treatment estimates for different outcomes.

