4.7 Missing data and outliers

A thorough data cleaning process will be carried out and attempts will be made to obtain any missing data by chasing until it is either received, confirmed as not available, or the study is at the analysis stage. Where data is unobtainable, all summaries will indicate how many missing results there are, by sequence, where any imbalances can be explored. Where data points are identified

as possible outliers both statistically and clinically, and are considerable in number, sensitivity analyses may be considered for the primary outcomes.

5. References

1. Schulz, K.F., et al., *Consort 2010 statement: Updated guidelines for reporting parallel group randomized trials*. *Annals of Internal Medicine*, 2010. **152**(11): p. 726-732.

6. Revision history

Version 1 of the SAP should be signed off by relevant personnel before any data analysis is carried out. If changes need to be made to v1.0 before this time, possibly due to emerging methodologies, these changes should be documented in Table 1 below, with new version number, date and a summary of the changes with justification(s). If any changes to the methodologies are required after data analysis has begun, these should be documented in the final analysis report in a chronological manner, documenting all decisions made and their justification(s).

Table 1 SAP revision history

Version number	Revision date	Justification for revision

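### The SAP has the study statistician unblinded after phase 1 to assess efficacy, which contradicts its own blinding statements, and the look is described nowhere else in the SAP

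*SAP*

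**What the plan says.** All references are to the SAP.

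- **Section 1.2.1 (Summary)** sets the time, "Once the participants have completed the first phase of treatment", and the action: "the study statistician will be unblinded to the treatment arms and will then assess whether or not there is evidence of efficacy of bezafibrate". The outcome named is the primary one, peak VO2. The same section describes a two-period crossover in which each participant next takes the other treatment, and says that participants and research staff do not know the order.
- **Section 2.5 (Blinding)** includes BTC staff among those blinded: "all BTC staff will be unaware of the allocation order". It makes no exception.
- **Section 4.1 (General considerations)** settles where the statistician sits: "Statistical analysis is the responsibility of the BTC study statistician".
- **Section 2.2 (Randomisation)** says of the random sequence that it "will be concealed from all clinical and research personnel".
- **Section 3.3.2 (Per-protocol population)** has the proportion of deviators judged "through a blinded examination of the population at the time of analysis by the study statistician", together with other members of the TMG.
- **Section 1.1.2 (Planned analyses and dissemination)** lists one end-of-study report after phase 2. Before that it lists only this: "Short blinded study update reports including safety and compliance will be produced and disseminated at regular intervals during the study".
- **Section 6 (Revision history)** says: "Version 1 of the SAP should be signed off by relevant personnel before any data analysis is carried out".

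**The concern.** The SAP gives opposite instructions on whether the person responsible for the primary analysis is blinded during phase 2. Following section 1.2.1 breaks section 2.5 and makes the blinded step in section 3.3.2 impossible.

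Blinding matters here because the SAP leaves several choices to judgement. Section 4.5.1 allows interactions to be explored where needed and other methods to be sought if model assumptions look invalid. Section 3.3.2 says that a complier-average analysis will be considered if more than 20% of participants are major deviators. Section 4.7 says that outlier sensitivity analyses may be considered. With about 12 participants, one such choice can move the estimate. Under section 1.2.1 the statistician would make these choices already knowing each participant's sequence and having seen a phase 1 comparison.

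The look also has no counterpart elsewhere in the SAP: no model, significance level, recipient or consequence. If it could support a claim of efficacy, it would be a second test of the primary outcome, and section 4.1 makes no adjustment for multiple testing.

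**Working it through.** **1. The statements side by side**

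| Question | Section 1.2.1 | Other sections |
|---|---|---|
| Does the statistician know the arms after phase 1? | Yes | No: 2.5 with 4.1; also 2.2 |
| Is the statistician blinded when deviators are judged at the time of analysis? | Cannot be | Yes: 3.3.2 |
| Is efficacy assessed before phase 2 ends? | Yes | Not listed in 1.1.2; no method in section 4 |

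**2. What unblinding at phase 1 discloses**

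There are two treatments and two periods, and each participant takes the other treatment in phase 2. The phase 1 arm therefore fixes the phase 2 arm, so the statistician learns the whole sequence of every participant.

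**3. The plan's own power figure**

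This is needed only to set an effect size for step 5. Section 2.4 gives 12 participants, two-sided 5%, and 0.90 SD for 80% power or 1.05 SD for 90%. For a paired t-test with 11 degrees of freedom, the noncentrality is d√12, with d in SDs of the within-subject difference.

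- d = 0.90: power 81.0% (80.2% with 10 degrees of freedom, after adjusting for period).
- d = 1.05: power 91.1% (90.5%).

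The figures reproduce on that scale. They do not reproduce in within-subject SDs, which is how section 2.4 labels them: d = 0.90/√2 gives 52.0% and d = 1.05/√2 gives 64.9%. That is a separate matter. For step 5 I take 0.90 SD of the difference, which is 0.90 × √2 = 1.27 within-subject SDs.

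**4. Type I error if the look counts**

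Assumptions, none of them stated in the SAP:
- the phase 1 look is a two-sample t-test at 5% (6 v 6, from the 1:1 allocation);
- the final test is a period-adjusted crossover test at 5%;
- a significant result at either would support a claim;
- the within-participant correlation ρ lies between 0 and 0.9.

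If the two tests were independent, the chance of at least one false positive would be 1 − 0.95² = 9.75%. Simulation under the null (100,000 trials per setting, 12 participants) gives:

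| ρ | 0 | 0.3 | 0.5 | 0.7 | 0.8 | 0.9 |
|---|---|---|---|---|---|---|
| Either test significant | 8.6% | 9.1% | 9.1% | 9.4% | 9.7% | 9.6% |

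With 15 participants (7 v 8) the range is 8.5% to 9.7%. Without the look, or if the look cannot support a claim or stop the trial, the final test stays at 5%.

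**5. How informative the look would be**

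For 6 v 6 with 10 degrees of freedom, the standardised effect is 0.90 × √2 × √(1 − ρ) and the noncentrality is that value × √3. For example, at ρ = 0.5 the effect is 0.90, the noncentrality is 1.56 and the power is 29%.

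| ρ | 0 | 0.5 | 0.7 | 0.8 | 0.9 |
|---|---|---|---|---|---|
| Power of phase 1 test, unadjusted | 51% | 29% | 19% | 15% | 10% |

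The full crossover has about 80% for the same effect. Section 4.4.1 has peak VO2 measured at baseline. A simulated analysis of covariance on baseline, with baseline correlated with phase 1 at the same ρ, has about 30% power at ρ = 0.7 and 27% at ρ = 0.9.

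**The case against.** The strongest case on the other side is that this is a wording conflict with limited consequences.

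- **The look is announced.** Section 1.2.1 gives its timing, who does it and on which outcome. This stands: a reader might call the look unplanned, but the fair word is unspecified.
- **Details may be in the protocol.** Section 1.1.1 limits the SAP to final analyses outlined in the protocol, which is not at hand. The absence of a boundary or recipient is therefore not, on its own, a fault in the SAP. It does not remove the contradiction, because no protocol text can make sections 1.2.1, 2.5 and 3.3.2 of this SAP agree.
- **Only the statistician is unblinded.** A reader might infer that the trial as a whole loses its blind. The SAP does not support that. Nothing says that participants, clinicians or assessors are told, and section 1.2.1 itself keeps participants and research staff unaware of the order.
- **The error inflation is hypothetical.** A reader might infer that the false-positive rate is already near 10%. The SAP states neither a 5% test at phase 1 nor a rule that such a test could support a claim. Its one specified primary analysis uses both periods. This stands, so the figure must remain conditional.
- **The discretion is bounded.** Major deviators are defined by a list and judged without reference to outcome data, together with other TMG members. Outlier handling is an optional sensitivity analysis, and section 6 requires sign-off before any analysis and a record of later changes. These safeguards reduce the harm. The main freedom left is the move to other methods in section 4.5.1.
- **The look is not worthless.** A reader might infer that it has almost no power. That holds only at high correlation without baseline adjustment, and the SAP gives no correlation.

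The sentence might also be a loose description of unblinding at the end of the study. It names the first phase, however, so on that reading it is misworded and still has to change.

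**Conclusion.** The contradiction is real and needs no assumption: section 1.2.1 cannot be followed together with sections 2.5 (read with 4.1) and 3.3.2. That unblinding at phase 1 discloses every full sequence to the statistician follows from the crossover design.

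The size of any bias from the open analysis choices cannot be computed from the document. The effect on type I error is conditional. It would be about 8.6% to 9.7% for 12 participants if each look were tested at 5%, either could support a claim, and the correlation lay between 0 and 0.9. It would be 5% if the look carried no claim or stopping rule. The look would be weak compared with the full crossover, but how weak depends on the correlation and on whether baseline is used.

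The wording should be corrected before any unblinded data reach the statistician.

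**What to change.** **Preferred.** Delete the sentence in section 1.2.1. State in section 2.5 that the study statistician stays blinded until phase 2 is complete, deviators have been classified, the SAP is signed and the database is locked, and that efficacy is tested once, after that.

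**If a look is truly intended.** Assign it to a separate unblinded statistician who takes no part in the final analysis decisions. State its purpose, method, significance level and recipient, and what may follow from it. If it can support a claim, share the 5% between the looks. As an illustration only, 0.001 at the look and 0.049 at the end gave a simulated overall error of about 4.9% to 5.1%, which is 5% within simulation error. Then make sections 1.1.2, 1.2.1, 2.2, 2.5 and 3.3.2 agree.

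**Cost.** The first option changes wording and gives up an interim impression of efficacy that no other section of the SAP uses. The second also needs a second statistician. In either case, check the protocol for matching text. If the look is described there, the protocol must change too, so the cost may extend beyond the SAP.

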1.2.2 Aims and objectives

It is hypothesised that bezafibrate will modify the cellular ratio of monolysocardiolipin to L4-cardiolipin, ameliorating disease phenotype in those living with the disease, providing the drug is free of significant side-effects at clinically effective doses.

It is also hypothesised that bezafibrate (and/or resveratrol in-vitro) may have beneficial effects independent of any effect on cardiolipin ratio due to their abilities to influence a range of mitochondrial pathologies.

The major questions to be answered are as follows:

1. What is the effect on biochemical/clinical outcome measures and quality of life of bezafibrate treatment in comparison to placebo in Barth syndrome?
2. Is it possible to correlate clinical improvements with *in vitro* analysis of cardiolipin ratio/profile and mitochondrial morphology in each participant's cells when exposed to bezafibrate in laboratory culture? How does this contrast with an *in vitro* response to resveratrol exposure? This could indicate whether a trial examining the efficacy of resveratrol may be required in the future to determine the optimal choice of drug.
3. What are the most feasible methods and standardised outcome measures that may allow better conduct of future trials (e.g. larger multinational trials) and evaluations in Barth syndrome?
4. Is it possible to create a research infrastructure which optimises recruitment, retention and communication with families and people with Barth syndrome?
5. What are the participant and family perceptions of research and any important potential barriers to participation?

The primary outcome to be measured is whole body oxygen consumption during peak bike ergometry exercise (i.e. peak VO_2). Improved quality of life is an overarching goal, principally through improved muscle function and is an important secondary outcome. A broad range of biochemical, mitochondrial and clinical readouts has also been selected as secondary outcome measures (see section 4.6) including cardiolipin ratio on which this work is predicated.

2. Study methods

2.1 Design

This study is a double-blinded, randomised, placebo-controlled crossover study. Treatment will be given in two 4-month long phases and a one month washout period between these where no treatment is given. Participants will be followed up as part of the study for one month after the end of second treatment period (bezafibrate or placebo).

2.2 Randomisation

A randomisation list will be created, numbered by study ID, with a 1:1 ratio of the allocations: bezafibrate followed by placebo, or placebo followed by bezafibrate. The allocation will be according to permuted block randomisation, with blocks of varying size. This list of study IDs and corresponding medication order will be provided to the clinical trials pharmacy department.

N.B. This method of randomisation does not comply with the requirement of an internet-based randomisation system supplied by an MHRA approved provider (e.g. Sealed Envelope) as described in the Bristol CTEU SOP ST 005 'Development of a Randomisation System', but an internet-based system was thought to be prohibitively expensive for so few patients.

Once a participant has given consent and eligibility has been documented and confirmed, they will be allocated to the next consecutive study ID. A doctor will prescribe the study 'medication' and the pharmacy will dispense the appropriate intervention given the participant's study ID and phase of the trial.

Allocation concealment will minimise selection bias. The sequence of random allocations will be generated by computer and will be concealed from all clinical and research personnel.

2.3 Framework

The difference between the treatments will be compared according to a superiority framework.

2.4 Sample size

This is a single centre study to be performed in patients attending the NHS National Barth Syndrome Service. A total of 18 males aged between six and 24 years currently attend the service. We anticipate that between 12 and 15 UK patients are likely to consent to take part.

In a simple crossover trial (a single intervention and control comparison), the standard deviation (SD) of the within subject difference between treatments is given as: square root of 2 times the within subject SD. In a crossover trial, all participants act as their own control.

In this trial, the difference in mean peak volume of O₂ consumption between placebo and bezafibrate phases will be tested, assuming a 2-tailed type I error of 5%. For a sample size of 12 participants, the trial will be able to detect a difference of 0.90 (within subject) SDs with 80% power, or 1.05 SDs with 90% power.

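### The detectable differences of 0.90 and 1.05 are labelled as within-subject SDs, but they give 80% and 90% power only as SDs of the paired difference

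*SAP*

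**What the plan says.** SAP section 2.4 (Sample size) first sets out the variance relation for a simple crossover: "the standard deviation (SD) of the within subject difference between treatments is given as: square root of 2 times the within subject SD". It then gives the trial's power statement for peak VO₂, "assuming a 2-tailed type I error of 5"%. "For a sample size of 12 participants", it says, "the trial will be able to detect a difference of 0.90 (within subject) SDs with 80% power, or 1.05 SDs with 90% power".

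The unit is printed beside 0.90 only, and 1.05 inherits it. The section gives neither an SD nor a target difference in ml/kg/min, so the multiple and its unit carry the whole claim. It also says that 18 patients attend the service and that 12 to 15 are expected to consent.

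**The concern.** The section introduces two quantities and ties them together by a factor of √2. It then quotes the detectable effects in the smaller one. If the authors calculated in SDs of the paired difference, the label drops the √2 they had just introduced. If they meant the label, the power is much lower than stated.

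The unit matters because this is the SAP's only statement of what the trial can detect. The SD that a reader is most likely to have for peak VO₂ is a test-retest, that is, within-subject SD. Multiplying it by 0.90 as the text invites gives a difference that the trial has roughly an even chance of missing, not a one-in-five chance. With 12 to 15 participants a non-significant result is a real possibility, and this sentence would be used to interpret it.

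**Working it through.** **Inputs**
- n = 12, two-sided α = 0.05, effects 0.90 and 1.05, stated power 80% and 90% (SAP 2.4).
- SD of the paired difference: SD_diff = √2 × SD_within (SAP 2.4).
- Two-period crossover, 1:1 to the two sequences (SAP 2.1 and 2.2), with period as a fixed effect (SAP 4.5.1). This gives n − 2 = 10 degrees of freedom. A plain paired t-test, with 11, is shown for comparison.

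**Formula.** Power = P(|T| > t_crit), where T is non-central t with non-centrality λ = √n × δ / SD_diff. For n = 12, √n = 3.464. The critical value is 2.228 (10 df) or 2.201 (11 df).

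**Step 1: reproduce the plan's figures, with the effects as multiples of SD_diff**

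| δ / SD_diff | λ | Power, 10 df | Power, 11 df | Stated |
|---|---|---|---|---|
| 0.90 | 3.118 | 80.2% | 81.0% | 80% |
| 1.05 | 3.637 | 90.5% | 91.1% | 90% |

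Both pairs reproduce. Solved exactly, the detectable effects are 0.898 and 1.040 (10 df), or 0.889 and 1.029 (11 df).

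**Step 2: take the label as printed, with the effects as multiples of SD_within.** Then δ / SD_diff = 0.90/√2 = 0.636 and 1.05/√2 = 0.742.

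| δ / SD_within | λ | Power, 10 df | Power, 11 df | Stated |
|---|---|---|---|---|
| 0.90 | 2.205 | 51.3% | 52.0% | 80% |
| 1.05 | 2.572 | 64.1% | 64.9% | 90% |

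**Step 3: what 12 participants can detect in within-subject SDs.** At 80% power: 0.898 × √2 = 1.27. At 90% power: 1.040 × √2 = 1.47. Multiplying the SAP's rounded 1.05 by √2 gives 1.48.

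**Step 4: could another method rescue the printed label at n = 12?**

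| Method | Power at 0.90 | Power at 1.05 |
|---|---|---|
| Two-sided normal approximation | 59.7% | 73.0% |
| One-sided t, 11 df | 66.3% | 77.8% |
| One-sided normal | 71.2% | 82.3% |
| Two-sample t, 12 per arm | 55.9% | 69.1% |

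None reaches 80% and 90%.

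**Step 5: could more participants rescue it?** With n − 2 df, power at 0.90 and 1.05 within-subject SDs is 62.6% and 75.8% for n = 15, and 71.7% and 84.0% for n = 18, the whole service. For 80% power at 0.90, 21 participants give 79.0% and 22 give 81.0%, so 22 are needed. The same number is needed for 90% power at 1.05.

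**The case against.** The strongest reply is that this is a wording slip and not a loss of power. The figures reproduce in SDs of the paired difference, the paragraph before has just discussed that SD, and the parenthesis may be shorthand for it. On that reading 80% and 90% stand. This is probably what happened, and it means that 51% and 64% apply only if the label is taken literally. It does not remove the error: the section itself uses "square root of 2 times the within subject SD" to separate the two quantities, so a reader who follows its definitions must take 0.90 in the smaller unit.

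A second reply is that 51% and 64% depend on the test assumed. Section 2.4 names no test, and section 4.5.1 compares nested models by likelihood ratio. A simulation of that test with 12 complete participants gave about 62% and 74% under the printed label, with a type I error near 8%. The exact shortfall therefore does depend on the test, but every version falls well short of 80% and 90%.

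A third reply is that little hangs on the sentence. Enrolment is set by the number of patients available, the SAP states no target difference, and the primary model, populations and significance level are untouched. All of this is true. It limits the damage to how the trial's sensitivity is described and how a null result is read. It also means that the figure of 22 participants shows the scale of the error and is not a recruitment target.

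**Conclusion.** The power sentence is wrong as written. Under the section's own definitions, 0.90 and 1.05 are SDs of the paired difference and not within-subject SDs. In the printed unit the detectable difference is understated by a factor of √2: it should be 1.27 for 80% power and 1.47 to 1.48 for 90%, about 41% larger. Read literally, the stated 80% and 90% become about 51% and 64%, a shortfall of 29 and 26 percentage points.

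These figures assume 12 participants with complete data in both periods, a two-sided 5% t-test and 10 degrees of freedom; using 11 changes power by about one point. If the authors calculated in SDs of the paired difference, as the match on both pairs suggests, only the unit needs correcting.

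**What to change.** Replace the sentence in SAP section 2.4 with: *With 12 participants and a two-sided 5% test, the trial can detect a treatment difference of 0.90 (80% power) or 1.05 (90% power) SDs of the within-participant difference, equivalent to 1.27 or 1.48 within-subject SDs.* This wording is right whichever unit the authors had in mind.

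The cost is one sentence, recorded in the SAP revision history. Enrolment, data collection and analysis stay as they are. The only loss is that the trial's sensitivity, in within-subject SDs, looks less favourable than the present text suggests.
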